### **Corticosteroid Requirement Changes over Time:**

Systemic corticosteroid therapy for cGVHD will be monitored throughout the study. The corticosteroid dose level will be measured by the daily dose amount versus the weight of subject (mg/kg/day). For the days without weight measurement, the last observed weight measurement will be used. Considering the frequency of corticosteroid use might not be once daily, we use weekly average daily dose instead of the actual daily dose. The average corticosteroid dose level in each week is calculated by

$$\text{Sum of total corticosteroid dose used in this week} / 7$$

If a subject terminated the study drug in the middle of the week, the average corticosteroid dose level in that week will be calculated by

Sum of total corticosteroid dose used in the week before the study drug termination / actual days in the week up to the last dose of study drug.

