4.1. Inclusion Criteria

Each potential subject must satisfy all of the following criteria to be enrolled in the study:

1. Steroid dependent/refractory cGVHD defined as modified NIH criteria (2014) below at any time post-HCT:
 - a. Dependent disease - defined when glucocorticoid (prednisolone doses ≥ 0.25 mg/kg/day or ≥ 0.5 mg/kg every other day) are needed to prevent recurrence or progression of manifestations as demonstrated by unsuccessful attempts to taper the dose to lower levels on at least 2 occasions, separated by at least 8 weeks.

In case of inability to taper the dose to ≤ 0.25 mg/kg/day or ≤ 0.5 mg/kg every other day (prednisolone doses) due to recurrence or progression of cGVHD manifestations, it is considered as steroid-dependent disease if the lowest tapering dose of the second occasion is equal or higher than the lowest tapering dose of the first occasion.
 - b. Refractory disease - defined when cGVHD manifestations progress despite the use of a regimen containing glucocorticoid (prednisolone at ≥ 1 mg/kg/day for at least 1 week) or persist without improvement despite continued treatment with glucocorticoid (prednisolone at ≥ 0.5 mg/kg/day or 1 mg/kg every other day) for at least 4 weeks.
2. Subjects must be receiving baseline systemic glucocorticoid therapy for cGVHD at study entry. The dose of steroids must be stable for 14 days prior to starting ibrutinib.
3. At the time of trial enrollment, participants may be receiving other immunosuppressive therapies in addition to glucocorticoids. Immunosuppressant doses must be stable for

14 days prior to starting ibrutinib.

4. Clinically stable or worsening cGVHD for a minimum of 14 days between screening and Day 1 cGVHD response assessment.
5. Male or female ≥ 12 years of age.
6. Karnofsky or Lansky (subjects <16 years) performance status ≥ 60 (see [Attachment 2](#)).
7. Adequate hepatic and renal function as defined as:
 - a. Aspartate aminotransferase (AST), alanine aminotransferase (ALT) $\leq 3 \times$ upper limit of normal (ULN), (unless of nonhepatic origin). If AST/ALT increase is associated with cGVHD then $\leq 5 \times$ ULN is acceptable
 - b. Total bilirubin $\leq 1.5 \times$ ULN (neither nonhepatic origin nor due to Gilbert's syndrome)
 - c. Estimated Creatinine Clearance ≥ 30 mL/min (Cockcroft-Gault formula)
8. Adequate hematological function defined as:

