## **2.5. Baseline**

Baseline is defined as the last observation on or prior to the first study drug administration.

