**Table 1: Demographic and Baseline Characteristics Variables**

Continuous Variables:	Summary Type
Age (years)	Descriptive statistics (N, mean, standard deviation [SD], median and range [minimum and maximum].)
Weight (kg)	
Height (cm)	
Baseline hemoglobin (g/L)	
Baseline platelets ( $10^9/L$ )	
Baseline Absolute neutrophil count ( $10^9/L$ )	
Baseline Bilirubin	
Categorical Variables	
Sex (male, female, unknown,undifferentiated)	Frequency distribution with the number and percentage of subjects in each category.
Race (Asian)	
Ethnicity (Hispanic or Latino, not Hispanic or Latino)	

Following baseline disease characteristics information will be summarized for all treated subjects:

- cGVHD Disease State (Steroid Dependent, Steroid Refractory)
- Overall Severity of cGVHD (1, 2, 3, NA)
- Months from Last Transplantation to Enrollment, which is defined as the time period between the last transplantation and enrollment
- Months from Initial cGVHD Diagnosis Date, which is defined as the time period between the initial cGVHD diagnosis and enrollment
- Months from Transplantation to initial cGVHD diagnosis date
- Karnofsky performance status score at baseline
- Lansky performance status score at baseline
- Number of prior cGVHD treatment regimens
- Organs involved in cGVHD
- Daily Steroid Dose per Weight at baseline (mg/kg/day)

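### The SAP's 7-day steroid average misstates an unchanged alternate-day regimen by 14.3% in every full week, and no steroid-specific baseline is defined to measure change against

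*SAP*

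**What the plan says.** SAP 5.3.1 measures systemic corticosteroid use in mg/kg/day and explains why it averages: "Considering the frequency of corticosteroid use might not be once daily, we use weekly average daily dose instead of the actual daily dose". The weekly value is "Sum of total corticosteroid dose used in this week" divided by 7. If study drug stops in mid-week, the divisor becomes "actual days in the week up to the last dose of study drug". SAP 5.3.2 summarises the result descriptively, separately for responders and non-responders.

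Protocol 4.1, criterion 1a, defines steroid dependence with paired thresholds: "prednisolone doses ≥ 0.25 mg/kg/day or ≥ 0.5 mg/kg every other day". Criterion 1b does the same, pairing 0.5 mg/kg/day with 1 mg/kg every other day. Criterion 2 adds: "The dose of steroids must be stable for 14 days prior to starting ibrutinib".

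On baseline, SAP 2.5 gives one general rule: "Baseline is defined as the last observation on or prior to the first study drug administration". SAP 4.1 lists a baseline characteristic with mg/kg/day as its unit, but no derivation. SAP 5.3.1 has no baseline rule of its own.

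**The concern.** The average exists so that non-daily regimens come out right. Every other day is the non-daily frequency that the eligibility criteria name, and a window with an odd number of days cannot hold a fixed number of alternate-day doses. An unchanged regimen therefore gives a weekly series that moves up and down.

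The endpoint is a change over time, so the reference value matters as much as the weekly value. Because the baseline derivation is not written down, two programmers could follow the SAP and report different changes from the same records. At stake is the steroid-sparing description in an open-label, single-arm trial planned for 17 subjects. At the assumed 60% response rate that is about 10 responders and 7 non-responders, so a few alternate-day subjects could visibly shift a group summary.

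**Working it through.** **Inputs.** Dose D = 0.5 mg/kg every other day (Protocol 4.1, 1a); window 7 days, or the actual days in a cut-short week (SAP 5.3.1); Day 1 is the first dose and there is no Day 0 (SAP 2.4). It is assumed that the weekly total adds doses on the calendar days they were taken, as SAP 5.3.1 reads, and that no dose is missed.

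**The protocol's own equivalence.** D/2 = 0.5/2 = 0.25 mg/kg/day. This reproduces the pairing in criterion 1a and is the value the measure should return. The documents give no error figure for the weekly average.

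**Full weeks.** With k doses in the week, the SAP value is kD/7.
- k = 3: 3 × 0.5/7 = 0.214; 0.214/0.25 - 1 = -14.3%
- k = 4: 4 × 0.5/7 = 0.286; 0.286/0.25 - 1 = +14.3%

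Between adjacent weeks, 4 to 3 doses gives 3/4 - 1 = -25% and 3 to 4 doses gives 4/3 - 1 = +33.3%. Weeks a multiple of 14 days apart hold the same count, so Weeks 1, 5, 9, 13, 17, 21, 25, 37 and 49 agree with each other and the false change among them is 0%.

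**Change from baseline, regimen unchanged.** Weeks 13, 25 and 37 begin on Days 85, 169 and 253. Counted from Day -7 with no Day 0, these are 84 + 7 = 91, 168 + 7 = 175 and 252 + 7 = 259 days later. All are odd, so each of these weeks holds the opposite count to the 7 days before Day 1.

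| Reading of baseline | Baseline (mg/kg/day) | False change at Weeks 13, 25, 37 |
|---|---|---|
| Daily equivalent of the regimen | 0.25 | -14.3% or +14.3% |
| Average of the 7 days before Day 1 | 0.286 or 0.214 | -25% or +33.3% |
| One dosing-day amount | 0.5 | 0.286/0.5 - 1 = -42.9%, or 0.214/0.5 - 1 = -57.1% |
| One off-day amount | 0 | percent change undefined |

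**Cut-short final week of n days.** For even n the count is exactly n/2 and the error is 0%. For odd n the count is (n - 1)/2 or (n + 1)/2, and the error is ±1/n: ±100% for 1 day, ±33.3% for 3 days, ±20% for 5 days. Weeks of 2, 4 or 6 days are correct.

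**Scale.** In the earlier study (Protocol 1.4.2) the responders' median fell from 0.29 to 0.24 mg/kg/day at Week 12: 0.24/0.29 - 1 = -17%. That is a shift in a group median and the figures above are within-subject, so the comparison indicates scale only.

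**Even window.** Fourteen days always hold 7 alternate-day doses: 7 × 0.5/14 = 0.25, error 0%, before and after Day 1.

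**The case against.** The strongest reply is that weekly averaging already does most of the work. A single-day dose of 0 or D is off by 100% from D/2; the average cuts that to 14.3%, and the error cancels over two weeks. The scheduled weeks from Week 5 on are all odd-numbered and consistent with each other. If dosing phase is arbitrary, the 3-or-4 count mainly adds noise to a group mean in mg/kg/day. Criterion 1a defines steroid dependence at any time after transplant, so it does not show that anyone is on alternate-day dosing during the study. The SAP plans no test, threshold or percent change for this endpoint. All of that stands, and it limits the consequence. It does not make the weekly value correct for the kind of regimen the rule was written to handle, nor does it supply a baseline.

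A reader might go further and infer from SAP 2.5 that baseline is the dose on one day, giving a false fall of 43% to 57% and a bias towards apparent steroid sparing. The documents do not support that as a fact. SAP 2.5 is generic; SAP 5.3.1 says a weekly average replaces the actual daily dose; and the mg/kg/day unit in SAP 4.1 also fits a daily equivalent. A one-way bias would further require that only dosing days count, because off days would give a baseline of 0. This is an undefined derivation, not a stated single-day rule.

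**Conclusion.** For an unchanged alternate-day regimen, the SAP 5.3.1 value is wrong by 14.3% in one direction or the other in every full week, and by more in final weeks of 1, 3 or 5 days. The false change from baseline is ±14.3% or -25%/+33% under the two averaging readings. The -43% or -57% figures apply only if a single dosing-day amount were used, which the SAP does not say. No single percentage range describes the problem, because the size depends on which weeks and which baseline are compared.

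The arithmetic is certain given strict alternate-day dosing and totals built from doses taken. The effect on the reported summaries is not known, because the documents do not give the share of subjects on such regimens; it could be nil. The endpoint is secondary and descriptive, and the response-rate decision rule does not depend on it. The change is worth making because the error is avoidable and the missing baseline rule leaves the result open to choice.

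**What to change.** In SAP 5.3.1, replace the 7-day sum divided by 7 with the sum over consecutive 14-day periods from Day 1 (Weeks 1-2, 3-4, and so on) divided by 14, covering the whole treatment phase. State which period is reported against each visit.

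Define the steroid baseline, both here and in SAP 4.1, as the sum over the 14 days before first dose divided by 14. This matches the stable-dose period in criterion 2.

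For a period cut short by stopping study drug, use the last even number of days up to the last dose, and say that no value is reported when only one day is available.

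The periods should be consecutive and not placed only at visits. Efficacy visits are 12 weeks apart from Week 13, so a visit-only window could miss a temporary steroid increase for a flare, and a 14-day window ending at the Week 2 visit (Day 8) would run back into baseline.

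The cost is SAP wording and a programming change on data the protocol already collects. The downside is slightly coarser time resolution during a taper or flare, and the loss of one day's data when a final period has an odd length.

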### **Change in Lee cGVHD Symptom Scale:**

Subject-reported improvement in symptom burden will be evaluated. The symptom burden is measured according to the Lee cGVHD Symptom Scale. There are 7 domains, and each has several items (refer to [Table 3](#)).

**Table 3: Lee cGVHD Symptom Scale**

Subscale	Related Items	Maximum No. of Missing Items to Get a Valid Score
Skin	1, 2, 3, 4, 5	2
Energy	14, 21, 22, 23, 24, 25, 26	3
Lung	12, 13, 15, 16, 27	2
Eye	6, 7, 8	1
Nutrition	11, 17, 18, 19, 20	2
Mouth	9, 10	1
Psychological	28, 29, 30	1

A score is calculated for each subscale by taking the mean of all items completed if more than 50% were answered and normalizing to a 0 to 100 scale. A total summary score is calculated as the average of these 7 subscales if at least 4 subscales have valid scores.

A change in  $\geq 7$  points on the Lee cGVHD Symptom Scale will be considered significant and relates to improvement in quality of life.

#### **5.3.2. Analysis Methods**

The all treated population will be used for all secondary efficacy endpoints.

Rate of sustained response for at least 20 weeks will be calculated with the exact 2-sided 95% confidence interval based on binomial distribution.

The DOR for responders will be calculated by the Kaplan-Meier method descriptively. Median DOR and the corresponding 95% confidence interval will be provided if estimable with Kaplan-Meier plot.

The overall cGVHD response rate at each timepoint of efficacy evaluation will be summarized by descriptive statistics.

Corticosteroid requirement changes over time will be summarized by descriptive statistics by responder (CR or PR) and non-responder.

Change in symptom burden measured by the Lee cGVHD Symptom Scale will be summarized by descriptive statistics. A summary of total scores as well as each subscale scores for Lee cGVHD symptom scale will be performed throughout the study. A summary of the proportion of subjects who have decreases of at least 7 points in Lee cGVHD symptom scale during the study will be performed.

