11. STATISTICAL METHODS

Statistical analysis will be done by the sponsor. A general description of the statistical methods to be used to analyze the efficacy and safety data is outlined below. Specific details will be provided in the Statistical Analysis Plan.

The primary analysis for all efficacy and safety endpoints will be conducted at the time when the last subject has completed the efficacy assessment at Week 37 or has discontinued treatment before Week 37. Final analysis will be conducted at the study end.

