### **1.4. Sample Size Justification**

With a sample size of 17 subjects and assuming an expected overall cGVHD response rate of approximately 60%, it is expected to have at least 80% power to show the efficacious treatment effect (the lower bound of 95% confidence interval of the response rate >25%). At least 1 adolescent subject (12-17 years of age) will be enrolled in this study.

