### **5. EFFICACY**

#### **5.1. Analysis Specifications**

##### **5.1.1. Level of Significance**

All tests will be 1-sided. The primary efficacy endpoint will be tested at the overall significance level of 0.025. For result presentation purpose, a 2-sided 95% confidence interval will be used.

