##### **5.2.2. Analysis Methods**

The all treated analysis set will be used for primary endpoint. The response evaluable analysis set will be used for sensitivity analysis.

The primary analysis for primary endpoint will be conducted at the time when the last subject has completed the efficacy assessment at Week 37 or has discontinued treatment before Week 37. Final analysis will be conducted at the study end.

The overall cGVHD response rate (CR + PR) and its 95% confidence interval will be calculated with the exact test for binomial distribution in the all treated population. The study is considered to be positive if the lower limit of the exact 2-sided 95% confidence interval based on binomial distribution exceeds the threshold value (0.25).

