#### 5.3.1. Definition

##### Sustained Response:

Sustained response is defined as NIH-defined response that sustain continuously for at least 20 weeks (140 days). Considering 7 days at maximum visit window allowed by protocol, the bound of sustained response is defined as 133 days. Intermittent SD assessment between response assessments is allowed.

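### At the Week 37 cut, ongoing late first responses in late-dosed subjects count as not sustained, so the 20-week sustained response rate at the primary analysis may be biased low

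*SAP*

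**What the plan says.** - **Definition.** The Sustained Response paragraph of SAP 5.3.1 starts from 20 weeks (140 days) and deducts a 7-day visit window: "the bound of sustained response is defined as 133 days". Stable disease between two response assessments does not break the response.
- **Analysis.** SAP 5.3.2: "Rate of sustained response for at least 20 weeks will be calculated with the exact 2-sided 95% confidence interval based on binomial distribution". The denominator for all secondary efficacy endpoints is the all treated population, and SAP 5.1.2 does not impute missing values. Neither section sets a minimum follow-up, a landmark or a not-yet-evaluable category.
- **Timing.** Protocol 11: "The primary analysis for all efficacy and safety endpoints will be conducted at the time when the last subject has completed" the Week 37 efficacy assessment, or has stopped treatment before it. A final analysis follows at study end.
- **Assessments.** The Time and Events Schedule places cGVHD assessments at Weeks 13, 25 and 37 and every 12 weeks after that. There is also one earlier on-treatment visit, read here as Week 5 because the table columns are hard to align.
- **Contrast.** For duration of response (DOR), SAP Table 2 censors a responder not known to have progressed or died by the data cutoff at the last adequate assessment. The analysis is by Kaplan-Meier.

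**The concern.** A proportion with a fixed denominator has two outcomes: shown to be sustained, or not. A response that is still ongoing but too recent to have lasted 133 days falls into the second group, together with responses that were really lost. The same subject is censored in the DOR analysis, so the two durability endpoints treat one situation differently.

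At stake is how the first reported durability figure is read. Protocol 3.2 says the study is meant to confirm that the earlier Phase 1b/2 results can be reproduced in Japanese patients. Protocol 1.4.2 reports that 20 of 28 responders (71%) in that study sustained a response for at least 20 weeks. The exact interval around the new rate reflects sampling error only and would not show a shortfall caused by short follow-up.

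**Working it through.** **1. The plan's own figures.** The bound is 20 × 7 − 7 = 133 days, as stated. The sample size also reproduces. With 17 subjects, the exact lower limit first passes 25% at 9 responders (0.278; 8 responders give 0.230). Power at a 60% response rate is then 80.1%, in line with "at least 80% power to show the efficacious treatment effect". The arithmetic below therefore uses 17 as the denominator.

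**2. Longest response observable by Week 37.** Day 1 of Week w is Study Day 7(w − 1) + 1, so the span between two visits is 7 × (later week − earlier week). Windows are those of Protocol 9.1.1: ±3 days up to Week 25 and ±7 days from Week 37.

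| First response | Span to Week 37 (days) | With windows | Reaches 133? |
|---|---|---|---|
| Week 5 | 224 | 214 to 234 | yes |
| Week 13 | 168 | 158 to 178 | yes |
| Week 25 | 84 | 74 to 94 (98 if ±7 applies at both visits) | no |
| Week 37 | 0 | 0 | no |

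**3. The visit each late responder needs.** A first response at Week 25 needs Week 49: 7 × 24 = 168 days. A first response at Week 37 needs Week 61 (168 days), because Week 49 again gives only 84 (at most 98).

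**4. Who lacks that visit at the cut.** A subject first dosed u weeks before the last subject has been followed to about Week 37 + u.
- Week 25 responders fall short if u is below 12.
- Week 37 responders fall short if u is below 24.

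This assumes that only scheduled assessments count and that the last subject's Week 37 visit sets the cut.

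**5. Cost per subject.** One truly sustained responder counted as not sustained lowers the rate by 1/17 = 5.9 points. With the approximately 20 subjects mentioned in SAP 1.2 it is 1/20 = 5.0 points.

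**6. Illustration on assumptions.** Take a true sustained rate of 0.60 × 20/28 = 42.9% and uniform accrual over A weeks. Let q25 and q37 be the shares of sustained responders who first respond at Week 25 and at Week 37. The fraction missed is q25 × 12/A + q37 × 24/A.

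- Low case, A = 78, q25 = q37 = 0.05: 0.0077 + 0.0154 = 0.023. The rate falls from 42.9% to 41.9%, a loss of 1.0 point or about 0.2 subjects of 17.
- High case, A = 26, q25 = 0.20, q37 = 0.10: 0.092 + 0.092 = 0.185. The rate falls to 34.9%, a loss of 7.9 points or about 1.4 subjects of 17.

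The accrual periods and the values of q25 and q37 are assumptions; the documents give none of them.

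**The case against.** The case against has several parts.

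- **The rule is inferred.** The SAP nowhere writes that an ongoing short response counts as not sustained. That is true, but a binary rate over all treated subjects, with no third category, leaves no other place for it.
- **Few subjects can be affected.** It takes both late enrolment and late first response. Anyone who responds by Week 13 can reach 133 days, even the last subject dosed. This stands, and it is why the bias is possible and not certain.
- **The shift is small beside the noise.** The exact 95% interval for 7/17 runs from 18% to 67%. This also stands, but the error goes in one direction only and the interval does not display it.
- **Other outputs cover it.** DOR is analysed at the same cut with censoring, subject listings are planned, and the final analysis can reclassify ongoing responses. This helps in part, but none of it corrects the rate at the cut. Protocol 10.1 also ends treatment and follow-up early if Japanese marketing approval is received.
- **Kaplan-Meier is no clean replacement.** SAP Table 2 censors at new cGVHD treatment, while SAP 5.2.1 requires response without new therapy, so the DOR curve may run high. It is also conditional on responders. Both points are correct, and the fix allows for them.

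A reader might go further and put a firm figure on the loss. For example, suppose 20 to 30% of responders first respond at Week 25 or later and a third of those are late enrolees. Then 0.60 × 0.20 to 0.30 × 1/3 gives 4 to 6 points. The documents support neither share, and the sum treats every affected subject as truly sustained. Applying 20/28 alone lowers it to 2.9 to 4.3 points.

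**Conclusion.** The timing follows from the schedule, and the plan has no rule for these subjects. Short follow-up can only remove sustained responders, so the 20-week rate at the primary analysis may be biased low as a measure of how many subjects achieve a sustained response.

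The size cannot be derived, because neither the accrual pattern nor the times of first response are given. It is zero if no late-dosed subject first responds at Week 25 or 37, 5.9 points for each truly sustained subject misclassified, and roughly 1 to 8 points in the illustration.

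Two stronger conclusions might be drawn, and the documents support neither. One is that the rate is certain to be understated; that depends on data not yet seen. The other is that the trial's main result is compromised. The success rule rests only on the overall response rate, and the sustained rate is a secondary, descriptive endpoint with no test or threshold. The point is still worth correcting, because the correction is cheap and the figure invites comparison with the earlier study.

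**What to change.** Amend SAP 5.3.2 as follows.

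1. At the primary analysis, keep the binomial rate over all treated subjects. Beside it, report the number of responders still in response with under 133 days of follow-up and, separately, the number who lost response before 133 days.
2. As a supplement, give the Kaplan-Meier probability of remaining in response at 133 days among responders. For this estimate, count new cGVHD treatment as an event instead of censoring it.
3. Name the final analysis as the definitive binomial sustained rate.

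The cost is SAP wording and a small amount of extra tabulation, with no new data and no protocol change. The supplementary estimate is conditional on responders, so it does not replace the all-treated rate and should be labelled accordingly.
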